#### **If Day and Month of AE start date are missing:**

If the start date has year, but day and month are missing, the 1st of January will be imputed

- If this date is earlier than the first dose date, then the first dose date will be used instead.
- If this date is later than the stop date (possibly imputed), then the stop date will be used instead.

#### **If Year of AE start date is missing:**

If the year of AE start is missing or AE start date is completely missing, then imputation will not be done.

If the AE end date (full or partial) is before the first dose date, then the AE should be considered as a pre-treatment AE. Otherwise, the AE will be considered as TEAE.

Missing dates for Concomitant medication will be imputed similarly as described above for AE.

### **7.3 Multiple Comparisons and Multiplicity**

Not Applicable

### **7.4 Adjustments for covariates**

Not Applicable

### **7.5 Multicenter Studies**

This is a single-center study.

### **7.6 Examination of Subgroups**

There is no planned subgroup analysis.

### **7.7 Coding Dictionaries**

Medical history and AEs will be coded using the Medical Dictionary for Regulatory Activities (MedDRA) version 23.0 or later. Medical procedures, prior and concomitant medications will not be coded.

## 7.8 Analysis Populations

### 7.8.1 Safety Population

All subjects who received study product will be included in the safety population and analyzed as treated.

### 7.8.2 Pharmacokinetic Analysis Population

The PK analysis population will consist of all subjects who received G03-52-01 injection and have sufficient evaluable PK samples for the reliable estimation of PK parameters for at least one of the monoclonal antibodies or serotypes A and B.

## 7.9 Subject Accountability

Summaries of analysis populations and subject disposition will be presented by each G03-52-01 cohort, Placebo (pooled across all cohorts) and overall will contain the following information:

- Number of subjects who are enrolled
- Number and percent of subjects who are randomized
- Number and percent of subjects who are dosed
- Number and percent of subjects who completed the study
- Number and percent of subjects who discontinued early and reason for early discontinuation
- Number and percent of subjects in the Safety and PK Analysis Population

This summary will be based on Enrolled Subjects.

Subject disposition and analysis populations, eligibility criteria satisfaction and consent information will be presented in listings.

## 7.10 Protocol Deviations

All protocol deviations captured will be listed by subject. These will be summarized by dose cohort and control group.

## 7.11 Subject Demographics and Baseline Characteristics

Subject demographics and baseline characteristics such as age, sex, race, ethnicity, height, weight, and Body Mass Index (BMI) will be summarized by dose cohort and control group. Individual subject demographics and baseline characteristics will be presented in listings. Demographics will be summarized for the Safety Population.

## 7.12 Medical and Surgical History

Medical history will be coded using the MedDRA, Version 23.0 or later and listed.

## 7.13 Other Baseline Characteristics

Not Applicable

## 7.14 Prior and Concomitant Medications

All concomitant procedures, prior and concomitant medications will be listed by subject.

## 7.15 Measurements of Treatment Compliance

As this is a single dose injection study, treatment compliance will not be separately summarized. It will be presented as part of drug administration listing.

## 7.16 Physical Examinations

All physical examination results will be presented in a subject listing.

## 7.17 Pharmacokinetic Analysis

PK parameters will be summarized by dose levels using descriptive statistics for each monoclonal antibodies (NX01, NX02, NX11, XB10, XB18, and XB23) and serotypes (A and B), separately. PK Analysis Population will be used for all listings, concentration summary, PK parameter summary and graphical presentation.

The individual sampling and subject concentration-time will be listed and displayed graphically on linear and semi-log scales. The concentrations will be summarized descriptively by nominal time point in tabular and graphical formats (linear and semi-log scales) for each monoclonal antibodies (NX01, NX02, NX11, XB10, XB18, and XB23) and serotypes (A and B), separately. Summary statistics (n, mean, SD, coefficient of variation [CV%], median, minimum, maximum, geometric mean and geometric CV%) will be calculated for each time point. Geometric CV% will be calculated as the square root of the exponentiated SD of the natural log transformed data (SQRT(exp(sln2)-1), where appropriate.

Pharmacokinetic parameters for each monoclonal antibodies (NX01, NX02, NX11, XB10, XB18, and XB23) and serotypes (A and B) will be listed and summarized descriptively, including n, arithmetic mean, SD, minimum, median, maximum, CV(%), geometric mean, geometric CV%. For  $T_{max}$ , only n, minimum, median, and maximum will be reported.

## 7.18 Pharmacodynamic Analysis

Not Applicable

## 7.19 Efficacy Analyses

Not Applicable

## 7.20 Biomarker Analysis

Not Applicable

## 7.21 Immunogenicity Analysis

Antidrug antibodies titers will be summarized by dose levels using descriptive statistics for each monoclonal antibodies (NX01, NX02, NX11, XB10, XB18, and XB23), separately. PK Analysis Population will be used for all listings, summary tables and graphical presentation.

The frequency and percentage of positive immunogenicity response will be summarized by dose levels. Anti-drug antibody status will be listed by subject over time, and percentage of subjects determined to be positive or negative summarized by dose levels at each available time point.

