## **6.2 Immunogenicity**

Immunogenicity will be assessed by the development of antibody titers. The presence of ADA will be evaluated over the course of the post-injection period.

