## 7. STATISTICAL METHODS

### 7.1 General

The statistical analysis will be conducted following the principles specified in the International Council for Harmonization (ICH) Topic E9 Statistical Principles for Clinical Trials (CPMP/ICH/363/96).

All statistical analyses will be performed using the statistical software SAS GRID Linux/SAS Studio and any exceptions will be detailed in the CSR.

All results collected in the database will be presented in listings. Both observed values and change-from-baseline values for each subject will be given where applicable. All continuous data will be listed with the same precision as presented in the database. Cohort, Subject ID, treatment and visit will be used to sort data listings.

Unless otherwise noted, continuous variables will be summarized using number of non-missing observations (n), arithmetic mean (mean), standard deviation (SD), median, minimum, maximum, lower quartile and upper quartile; categorical variables will be summarized using the frequency count and the percentage of subjects in each category.

In the data listings, study day relative to the study product dosing date for each cohort may be presented. Study day relative to dose will be calculated as: event date – study product dose date (+ 1 if event date  $\geq$  dose date).

All subjects who received placebo in each of the cohorts will be combined and presented along with the other dose levels until specified otherwise.

Baseline will be the latest available measurement prior to the study product dose date in each cohort.

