## **7.23 Planned Interim Analysis**

A blinded interim safety and PK analysis is planned for this study to analyze all PK, ADA, and MNA samples for Cohorts 1-3 through Day 60 and Day 120. This will include all subjects in all cohorts through Day 60 and Day 120. A second blinded interim safety analysis is planned to analyze all PK, ADA, and MNA samples for Cohort 4 through Day 90. Stopping criteria are for safety and are defined in Section 9.5 of the protocol.

The ICON PK scientist will be unblinded to the treatment assignment for that particular cohort to facilitate a more detailed assessment of the PK and ADA data, which may include individual patient demographic and safety data. The ICON PK scientist will provide a summary of the PK and ADA analysis, including individual patient data, but will not include the unique patient number to ensure the Investigators and Sponsor remain blinded or any other individual data that may unblind.

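### SAP 7.21 confines the ADA tables and listing to the PK Analysis Population, which leaves out placebo, and has no rule for a subject who is ADA-positive both before and after dosing

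*SAP*

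**What the plan says.** **Population.** For the immunogenicity outputs SAP 7.21 states: "PK Analysis Population will be used for all listings, summary tables and graphical presentation". The titles of Tables 14.2.2.1 (titers) and 14.2.2.2 (status) and of Listing 16.2.6.2 carry the same population. SAP 7.8.2 defines it as "all subjects who received G03-52-01 injection and have sufficient evaluable PK samples", and protocol 10.3.1 has the same restriction to the active product.

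**Sampling.** Protocol 7.2 takes the pre-dose ADA sample in every subject. Protocol 6.6.2 and SAP 3.12 set the later draws by cohort, not by arm. Placebo subjects therefore give the same ADA samples as active subjects in their cohort.

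**General rules.** SAP 7.1 says "All results collected in the database will be presented in listings", with no exception. On placebo it says "All subjects who received placebo in each of the cohorts will be combined and presented along with the other dose levels until specified otherwise". SAP 7.22 (safety) and 7.9 (disposition) repeat the pooling of placebo; SAP 7.17 (PK) and 7.21 (ADA) do not.

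**Response.** SAP 7.21 states: "The frequency and percentage of positive immunogenicity response will be summarized by dose levels". It also plans ADA status by subject over time and percentages positive and negative at each time point. The nearest text to a definition is SAP 6.2: "Immunogenicity will be assessed by the development of antibody titers". That section places the evaluation of ADA in the period after injection. Neither section says how a subject already positive before dosing enters the overall response.

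**The concern.** Immunogenicity is part of the secondary objective, and ADA is a secondary endpoint for all cohorts. Two things stand out.

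First, the population chosen for ADA depends on having received active product and on having an evaluable PK profile. Neither condition is needed to read an ADA result. The placebo subjects are the only concurrent group that can show how often the assay reads positive after injection without the drug, and they have no place in the planned ADA tables or listing. An active subject who gave ADA samples but lacks enough evaluable PK samples is lost as well.

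Second, the overall positive rate by dose can mix antibody that was there before dosing with antibody that arose after it. The possibility is not remote in kind: protocol 2.2 mentions a few subjects with pre-existing antibodies in the study of a similar product. Without a rule, the treatment of such subjects would be settled after the data are seen.

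**Working it through.** **1. Check the schedule against the plan's own figure.** Protocol Table 2 gives an ADA blood volume of 42 mL per subject in Cohorts 1-3 and 36 mL in Cohort 4. Protocol 6.6.2 gives 6 mL per draw.
- Cohorts 1-3: pre-dose and Days 15, 30, 45, 60, 90, 120 = 7 draws; 7 x 6 = 42 mL.
- Cohort 4: pre-dose and Days 45, 60, 90, 120, 180 = 6 draws; 6 x 6 = 36 mL.

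Both figures reproduce, so the draw counts are sound.

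**2. Count what the PK Analysis Population leaves out.** SAP Table 3-1 plans 8 active and 2 placebo in each of four cohorts: 32 active, 8 placebo.

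| Group | Cohorts 1-3 | Cohort 4 | Total samples |
|---|---|---|---|
| Active | 24 x 7 = 168 | 8 x 6 = 48 | 216 |
| Placebo | 6 x 7 = 42 | 2 x 6 = 12 | 54 |
| All | 210 | 60 | 270 |

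Placebo share: 54/270 = 20%. Of the 54, 6 x 6 + 2 x 5 = 46 are post-dose. The ADA outputs in SAP 7.21 can cover at most 32 subjects and 216 samples. Active subjects without evaluable PK would reduce this further; their number cannot be known in advance.

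**3. Set the texts side by side.**
- *Listing.* SAP 7.1 promises that all collected results are listed and allows no exception. Listing 16.2.6.2 is limited to the PK Analysis Population. These contradict each other.
- *Tables.* The SAP 7.1 pooling sentence yields wherever another section specifies otherwise, and SAP 7.21 with its table titles does so. This is no contradiction. It is a choice, and its effect is that no planned ADA table shows a placebo rate.

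**4. Size of the missing response rule.**
- One subject positive both before and after dosing, counted or not counted: 1/8 = 12.5 percentage points in a dose group of 8. Because the ADA tables are split by antibody, this applies to the table of the antibody concerned.
- Example with one such subject and one subject who turns positive after dosing: 2/8 = 25.0% if both count; 1/7 = 14.3% if the rate is taken among subjects negative before dosing.
- The general baseline rule in SAP 7.1 does not close the gap. SAP 7.21 does not invoke it, and read literally it takes the last value before the dose date, which would leave out the Day 0 pre-dose draw. Footnote 14 of SAP Table 3-2 treats that draw as the baseline sample.

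**5. What a placebo column can carry.** Exact (Clopper-Pearson) 95% interval with n = 8: for 0/8 the upper limit is 1 - 0.025^(1/8) = 36.9%; for 1/8 the interval is 0.3% to 52.7%. It is a descriptive reference and cannot support a formal comparison.

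**The case against.** The best defence of the plan has four parts.

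- *The exclusion is allowed.* This stands for the tables, because the SAP 7.1 default yields to a specific section. It does not stand for the listing, since the listing sentence has no such clause.
- *Eight placebo subjects add little, and pre-dose samples from up to 32 active subjects already give a background rate.* The imprecision is real. But pre-dose samples show only the background before injection. The 46 post-dose placebo samples show how status varies over follow-up without the drug, and they cost nothing extra. Protocol 10.3.5 promises no placebo comparison, so this is a loss of information and not a broken commitment.
- *The response gap is small.* Largely granted. SAP 6.2 looks at the post-injection period, so a subject positive only before dosing is not a response. The by-visit status shows the pre-dose result for each PK-evaluable active subject, so a reader could recover the subjects who turned positive. What remains is the overall rate when a subject is positive at both times, and any titer-boost threshold.
- *The Cohort 4 sampling days are deliberate.* Granted. Cohort 4 has no Day 15 or Day 30 draw and adds Day 180, and the protocol and SAP state this consistently. It calls for a label at most.

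A reader might also infer a conflict with SAP 7.23, whose interims are "to analyze all PK, ADA, and MNA samples for Cohorts 1-3 through Day 60 and Day 120" and "analyze all PK, ADA, and MNA samples for Cohort 4 through Day 90". The documents do not support that: SAP 7.23 sets the scope of the interim looks, and a wider interim scope does not contradict narrower final outputs. A reader might likewise infer from protocol exclusion criterion 24 that Cohort 4 differs from the others in pre-dose ADA status. NX02 is one of the product's own antibodies, and footnote 5 of SAP Table 3-2 speaks of its level, so the criterion cannot be taken to concern antibodies against it.

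**Conclusion.** The point holds, and it should be fixed before the final analysis. Followed as written, SAP 7.21 leaves 8 of 40 planned subjects and 54 of 270 scheduled ADA samples (20%) out of the ADA tables and Listing 16.2.6.2, together with any active subject whose PK is not evaluable. The listing contradicts SAP 7.1; the tables do not, but they discard a reference already collected. The overall positive response can count pre-existing ADA as a response, worth 12.5 percentage points per subject in a group of 8.

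The counts assume full enrolment as planned, with no replacements and no missed draws. The 25.0% against 14.3% example is an illustration. How likely such a subject is cannot be stated, because the documents give no prevalence of pre-existing ADA for this product. Primary safety results are not affected.

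**What to change.** 1. In SAP 7.21, Tables 14.2.2.1 and 14.2.2.2 and Listing 16.2.6.2, replace the PK Analysis Population with the Safety Population (dosed subjects with ADA results). Add a pooled placebo column to the tables, shown descriptively. This also brings the listing into line with SAP 7.1.
2. Define the overall response against the Day 0 pre-dose sample. Report separately the baseline-positive subjects and the treatment-induced cases, meaning negative before dosing and positive after, with baseline-negative subjects as the denominator.
3. If a titer rise in a baseline-positive subject is to be reported as a boost, write the criterion and its source into the SAP before final unblinding. SAP 7.23 already unblinds a PK scientist to ADA data at the interims, which is a further reason to set it in advance.
4. Optionally, label any overall rate compared across doses with its sampling days, or show it also on the common Days 45, 60, 90 and 120.

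The cost is SAP wording, a population flag and output titles. The samples are already scheduled in all subjects, so no new procedures are needed.

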3.2.2. Secondary Endpoints

- The pharmacokinetic assessment of C_{max} , T_{max} and $AUC_{(0-t)}$ as measured by the validated Battelle Mouse Neutralization Assay (MNA) for serotypes A and B
 - Pharmacokinetic samples will be tested by MNA at pre-dose and on Days 4, 30, 60, 90, and 120 for Cohorts 1-3.
 - Pharmacokinetic samples will be tested by MNA at pre-dose, 2-hours post-dose (future use), and on Days 4, 30, 45, 60, 90, and 120 for Cohort 4.
- The assessment of C_{max} , T_{max} , half-life (α and β), MRT, and $AUC_{(0-t)}$ for each of the monoclonal antibodies of G03-52-01 as measured by a validated electrochemiluminescence assay (ECLA) or validated enzyme-linked immunosorbent assay (ELISA).
 - Pharmacokinetic samples will be tested by ECLA or ELISA at pre-dose, 2, 4, 8, 24, 48, and 72 hours post injection, and on Days 4, 8, 15, 30, 45, 60, 90, and 120 for Cohorts 1-3.
 - Pharmacokinetic samples will be tested by ECLA or ELISA at pre-dose, 6 hours post-dose, and on Days 1, 2, 4, 8, 15, 30, 45, 60, 90, 120, and 180 for Cohort 4.
- Samples will be tested to evaluate presence of anti-drug antibodies (ADA) collected for all cohorts.
 - Samples will be tested for ADA at pre-dose, 15, 30, 45, 60, 90, and 120 for Cohorts 1-3.
 - Samples will be tested for ADA at pre-dose and on Days 45, 60, 90, 120, and 180 for Cohort 4.

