6.6.2. Anti-Drug Antibody Assay

Six-mL samples of blood will be drawn pre-dose on Day 0, and on Days 15, 30, 45, 60, 90, and 120 for determining the presence of ADA using a validated ECLA that measures total anti-drug antibody in serum for Cohorts 1-3. This will be done to assess immunogenicity.

Six-mL samples of blood will be drawn pre-dose on Day 0 and on Days 45, 60, 90, 120, and 180 for determining the presence of ADA using a validated ECLA that measures total anti-drug antibody in serum for Cohort 4. This will be done to assess immunogenicity.

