### **3.10 Evaluation Pharmacokinetic and Sampling Schedule**

Six-mL samples of blood for PK samples will be drawn at the following times: pre-dose, and at 2, 4, 8, 24, 48, and 72 hours post dose and on Days 4, 8, 15, 30, 45, 60, 90, and 120 for cohorts 1-3 & pre-dose, at 6 hours post-dose, and on days 1, 2, 4, 8, 15, 30, 45, 60, 90, 120 and 180 for cohort 4. Serum will be analyzed for levels of each of the monoclonal antibodies using a validated ECLA or ELISA. All PK samples will be tested by ECLA or ELISA.

Three 10-mL samples of blood will be drawn to be analyzed for neutralizing antibody concentrated using the validated Battelle MNA. PK samples will be tested by the Battelle MNA for serotypes A and B at pre-dose and on Days 4, 30, 60, 90, and 120 for cohorts 1-3 & at pre-dose, and on days 4, 30, 45, 60, 90 and 120 for cohort 4.

PK samples will be collected as described in [Table 3-2](#).

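### ADA status is only positive or negative and is never read against the same-visit drug level, so the plan cannot tell a true negative from one masked by circulating drug.

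*SAP*

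**What the plan says.** SAP 7.21 plans two kinds of ADA output by dose. For titers: "Antidrug antibodies titers will be summarized by dose levels using descriptive statistics", separately for each of the six antibodies. For status, it plans the percentage with a positive response, a by-subject listing over time, and the "percentage of subjects determined to be positive or negative summarized by dose levels at each available time point". Table 14.2.2.2 carries the status summary. SAP 6.2 and Protocol 10.3.5 add only that ADA presence is followed after injection.

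Protocol 6.6.2 describes the assay as a means of "determining the presence of ADA using a validated ECLA that measures total anti-drug antibody in serum for Cohorts 1-3", with the same description for Cohort 4. No drug-tolerance level is given there or in SAP 3.12.

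The ADA schedules differ by cohort (Protocol 3.2.2): "Samples will be tested for ADA at pre-dose, 15, 30, 45, 60, 90, and 120 for Cohorts 1-3", and "Samples will be tested for ADA at pre-dose and on Days 45, 60, 90, 120, and 180 for Cohort 4".

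Drug concentrations are measured on all of these days. SAP 3.10 lists PK samples "on Days 4, 8, 15, 30, 45, 60, 90, and 120 for cohorts 1-3", and for Cohort 4 on days that include 45, 60, 90, 120 and 180. No section uses these concentrations to interpret an ADA result.

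**The concern.** The ADA assay looks for antibody against six IgG1 antibodies that may themselves still be in the serum sample. If circulating drug occupies the antibody being sought, a sample can read negative although ADA is present. How far this happens depends on the drug level in the sample and on the assay's tolerance for it.

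Under a two-way status such a sample enters the table as a negative. Immunogenicity of escalating doses is part of the secondary objective, and the table is laid out by dose. Drug level rises with dose, so any interference acts along the comparison the table invites. A flat or falling ADA rate with dose, or 0 of 8 at 100 mg, could then reflect low immunogenicity or masking. The planned summary could not separate the two.

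**Working it through.** The plan states no ADA rate, half-life or tolerance, so there is no figure to reproduce. The calculations below show what the missing rule could matter for, under stated assumptions.

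**1. Are paired data available?** (Protocol 3.2.2; SAP 3.10 and 3.12)

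| | Post-dose ADA days | PK sample on each? |
|---|---|---|
| Cohorts 1-3 (10, 25, 50 mg) | 15, 30, 45, 60, 90, 120 | Yes |
| Cohort 4 (100 mg) | 45, 60, 90, 120, 180 | Yes |

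The days common to all cohorts are 45, 60, 90 and 120.

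**2. Dose effect at matched visits.** Assume dose-proportional, first-order decline with half-life h: level ∝ dose × 2^(−t/h). At any shared day the 100 mg level is 10 times the 10 mg level. The delay until 100 mg reaches the same level is h × log2(100/10) = 3.32h. With h assumed at 14, 21 or 28 days this is 46.5, 69.8 or 93.0 days. No volume, bioavailability or tolerance is needed for this step.

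**3. What masking would do with 8 active subjects per dose.** Observed rate = true rate × (1 − masked share); P(0 of 8) = (1 − observed rate)^8. At an assumed true rate of 25%:

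| Masked share | Observed rate | P(0 of 8) |
|---|---|---|
| 0% | 25% | 0.10 |
| 50% | 12.5% | 0.34 |
| 75% | 6.25% | 0.60 |

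The masked share itself cannot be derived from the documents.

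**4. Does the ordering hold at each cohort's last visit?** Compare Cohort 4 at Day 180 with the others at Day 120. The ratio of residual drug is (dose ratio) × 2^(−60/h).

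| Cohort 4 Day 180 against | h = 14 | h = 21 | h = 28 | Ratio below 1 if |
|---|---|---|---|---|
| Cohort 3 Day 120 (ratio 2) | 0.10 | 0.28 | 0.45 | h < 60 days |
| Cohort 2 Day 120 (ratio 4) | 0.21 | 0.55 | 0.91 | h < 30 days |
| Cohort 1 Day 120 (ratio 10) | 0.51 | 1.38 | 2.26 | h < 18.1 days |

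At the last visit the highest dose does not necessarily carry the most drug.

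**5. Illustration in concentration units.** Protocol 2.2 splits 10 mg into 5 mg anti-A and 5 mg anti-B antibodies. An equal split within each triple is assumed, so each antibody is dose/6. One-compartment model: C = (dose/6)/(V/F) × ka/(ka − ke) × (e^(−ke·t) − e^(−ka·t)), with ke = ln 2/h. Assumed: ka = 0.3/day and V/F from 4 L (V 4 L, F 1.0) to 11.7 L (V 7 L, F 0.6). For h = 21 days, in µg/mL:

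- 10 mg: Day 45, 0.04-0.11.
- 100 mg: Day 45, 0.36-1.06; Day 60, 0.22-0.65; Day 90, 0.08-0.24; Day 120, 0.03-0.09; Day 180, 0.004-0.012.

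An arbitrary tolerance of 0.25 would make a Day 45 negative readable at 10 mg and not at 100 mg. By Day 90 the 100 mg samples are below it too. At h = 28 days, Day 90 at 100 mg spans 0.17-0.49, and Day 120 is at most 0.23. The highest 100 mg level at any Cohort 4 post-dose ADA visit across h = 14 to 28 days is 1.49 (Day 45, h = 28, V/F = 4 L). In this model, any tolerance above that leaves no masking in Cohort 4.

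**The case against.** The strongest reply is that no bias has been shown. Masking needs drug above tolerance, and the documents give neither quantity. The assay is validated and described as measuring total ADA, which may include drug-bound ADA, and its validation report is not among the documents. This stands: the point can only be conditional.

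Second, the schedule already protects Cohort 4 to some extent. It has no Day 15 or Day 30 ADA sample, its first post-dose sample is at Day 45, and it has an extra one at Day 180. Persistent ADA could be picked up late, and step 5 shows how quickly levels can fall. This also stands, and it limits the concern to visit-by-visit rates and to ADA that has gone by the later visits. The missing early samples make an ever-positive rate non-comparable across cohorts for a separate reason.

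Third, ADA status and concentrations are both listed by subject, and SAP 7.23 has the PK scientist look at PK and ADA data together at the interim. A careful reader could match them by hand. But without a stated tolerance there is no threshold to apply, and the summary table would still count the sample as negative. Titers do not rescue a masked negative either.

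Fourth, the ADA summaries are descriptive, with no test of dose response. That lowers the stakes but does not make the table interpretable.

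Finally, dropping inconclusive samples from the denominator creates its own bias: every positive stays while non-positives above tolerance leave. With 8 subjects all above tolerance and 1 positive, the rate becomes 1/1 = 100% instead of 1/8 = 12.5%. This is right, and it shapes the fix.

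**Conclusion.** The gap is real and cheap to close. As written, SAP 7.21 would report a negative taken while drug exceeds assay tolerance as a true negative, although the concentration needed to recognise it is scheduled on the same day. At matched visits this can lower the ADA rate more at higher doses. The 10-fold dose range corresponds to a lag of 3.32 half-lives, or 47 to 93 days at assumed half-lives of 14 to 28 days, within a 120- to 180-day sampling window. This rests on dose-proportional, first-order decline and on an assay that is sensitive to drug at the levels present.

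A reader might infer that the ADA rate is in fact biased downward as dose rises, or that 0% at 100 mg would be an artefact. The documents do not support either. They give no tolerance and no half-life for the product, the 0.25 µg/mL above is purely illustrative, and the ordering by dose need not hold at Day 180 against Day 120. The supportable statement is that bias is possible and the planned analysis could not show whether it occurred.

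**What to change.** In SAP 7.21 and Table 14.2.2.2:

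- State the validated drug-tolerance level of the ADA assay for each of the six antibodies.
- Report status in three categories: positive; negative (not positive, same-visit concentration at or below tolerance); inconclusive (not positive, concentration above tolerance).
- Count a reported below-quantification (BLQ) concentration as below tolerance, after confirming that the PK assay's quantification limit is not above it. Use the reported result, because SAP 6.1.2 sets BLQ values after the first measurable concentration to missing for summaries.
- Keep incidence among all evaluable subjects as the main rate and show the inconclusive count beside it. Give the conclusive-only rate as a sensitivity figure, labelled as biased upward.
- Compare doses by visit at the common Days 45, 60, 90 and 120.

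The cost is SAP wording and one merge of PK and ADA data already planned for collection, with no new sample or visit. The downside is that fewer samples may count as negative at earlier visits and higher doses. If tolerance proves high, the inconclusive count is zero and the negatives are better supported.
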